1. STUDY DESIGN

In this study we will evaluate the application of LESW for patients with IC/BPS. LESW with 2000 shocks, frequency of 3 pulses per second, and maximum total energy flow density 0.25 mJ/mm² or placebo (Shock Wave setting without shock wave energy transmission) will be applied to the suprapubic bladder region once a week for 4 weeks. Treatment parameters were modified from different urologic and non-urologic case studies and publications. The device used for the study was a standard electromagnetic shock wave unit with a focused shock wave source (LITEMED LM-ESWT-mini system, Taiwan). The focus zone penetration depth was in the range of 30–90 mm. This study was designed in a multicenter, randomized, double-blind, placebo-controlled trial to test the actual therapeutic effects of LESW on IC/BPS. The results of this study may provide clinical evidence for an alternative therapeutic regimen in the treatment of IC/BPS.

2. OBJECTIVE AND ENDPOINTS

The objective of this study is to evaluate the efficacy and safety of LESW for the treatment of IC/BPS.

The primary and secondary endpoints are described as shown below:

(1) Primary End-point (1 month)

The efficacy of LESW will be evaluated for:

Net changes of the O’Leary-Sant symptom score from baseline to 1 month after the treatment day.

(2) Secondary end-points

Efficacy

The efficacy of LESW will be evaluated for:

- (1) Net changes of the following parameters from baseline to 1 month after the treatment day: VAS, functional bladder capacity (FBC), voiding frequency at daytime and voiding frequency at night time as recorded in 3-day voiding diary.
- (2) Global response assessment (GRA) of therapeutic result by the patient (categorized from -3 to +3, indicating markedly worse to markedly improved) at 3 months after the treatment day.
- (3) Net changes of the maximum flow rate, voided volume, and PVR from baseline to 1 month after the treatment day.

(4) Changes of urinary nerve growth factor and cytokines level from baseline to 1 month after treatment day.

Effectiveness of treatment was considered if the patient has an improved GRA by 2 scales at the end-point assessments.

Safety

(1) Local adverse event incidences (hematuria, miction pain, UTI, urinary retention). The severity of adverse event is categorized as indicated below:

Severity of AE	Description
Mild	Transient and easily tolerable, not affecting usual daily activities
Moderate	Causes patient's discomfort, interrupting usual daily activities
Severe	Causes considerable interference with daily activities and may be incapacitating or life-threatening

(2) Systemic Adverse Events:

Any systemic adverse event occurring after LESW will be asked to report and patients will be properly investigated and treated. The cause for systemic adverse event may be not related with LESW.

(3) Changes in physical examinations.

(4) Changes in blood pressure and other laboratory test results will be examined if patients have severe adverse events or physical examinations reveal abnormalities.

(3) Follow-up (3 months)

Efficacy

The efficacy of LESW will be evaluated for:

- (1) Net changes of the following parameters from baseline to 1 month after the treatment day: VAS, functional bladder capacity (FBC), voiding frequency at daytime and voiding frequency at night time as recorded in 3-day voiding diary.
- (2) Global response assessment (GRA) of therapeutic result by the patient (categorized from -3 to +3, indicating markedly worse to markedly improved) at 2 months after the treatment day.
- (3) Net changes of the maximum flow rate, voided volume, and PVR from baseline to 2 months after the treatment day.
- (4) Changes of urinary nerve growth factor and cytokines level from baseline to 2 months after treatment day.

Effectiveness of treatment was considered if the patient has an improved GRA by 2 scales at the primary and secondary end-point assessments.

Patients who are not effective to the treatment at 2 months will receive repeated LESW treatment.

Safety

- (1) Local adverse event incidences (hematuria, miction pain, UTI, urinary retention) are reported.
- (2) Any systemic adverse event occurring after LESW will be asked to report and patients will be properly investigated and treated. The cause for systemic adverse event may be not related with LESW treatment.

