5. STUDY PROCEDURE

5.1. General Study Design

This study is designed as a double-blind, randomized, paralleled, controlled trial. The IC/BPS confirmed patients will be randomly assigned to receive (1) LESW or (2) placebo control group. The treatments will be evaluated at baseline screening and at least 2 study required visits (treatment visit and primary end-point evaluation visit) will be performed for symptom score recording, VAS, uroflowmetry studies, adverse event recording and global satisfaction assessments. Urine samples (30 ml) will also be collected at each visit for analysis of the urinary NGF and cytokines levels.

Procedures of LESW

Studied patients are requested to void completely before treatment. Urine samples (30 ml) will be collected for analysis of the urinary NGF and cytokines levels. The patients are placed in supine position in an examination room at out-patient clinic.

The shock wave applicator (“**LITEMED**” **LM-ESWT-mini system, Taiwan**) will be gently placed directly on the ultrasound transmission gel over the skin surface of suprapubic region above the urinary bladder weekly for 4 weeks, with 2000 shocks, frequency of 3 pulses per second, and maximum total energy flow density 0.25 mJ/mm². The current shock wave intensity and number used was modified from previous report [1, 2].

Patients will be asked about any painful sensation that they experience during the treatment. Vital signs (body temperature, blood pressure, heart rate and respiration rate) will be recorded at pre-treatment, and 30 mins following treatment. During the treatment, patient will be stayed in a treatment room and accompanied by a research assistant.

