7. STATISTICAL ANALYSIS

7.1. Evaluability

Patients receiving baseline screening and treatment will be considered as intent-to-treat (ITT) population. The ITT population with the following conditions will be considered as per-protocol (PP) population:

- 1. Not taking any prohibited medications
- 2. Fulfilling all entry criteria
- 3. Have treatment visit and post-treatment evaluations on the primary endpoint

The efficacy evaluation will be performed on both the ITT and PP datasets while the safety evaluations will be performed only on the ITT datasets. The primary conclusions will be made for the primary and secondary endpoints on the ITT patients.

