7.2 Analysis

The statistical objective of this study is to demonstrate that the efficacy of LESW is superior to placebo with respect to the decreases of O'Leary-Sant symptom score, VAS, increase in functional bladder capacity and improvement in GRA. The safety profile of LESW or placebo for the either group of intravesical treatment of patients with IC/BPS will also be confirmed.

Primary Efficacy Endpoint

The efficacy of LESW treatment will be evaluated for:

(1) Net change of the O'Leary-Sant symptom score from baseline to 1 month after the treatment day.

Secondary Efficacy Endpoint

The efficacy of LESW will be evaluated for:

- (1)Net change of the following parameters from baseline to 1 month after the treatment day: Visual analog score (VAS) for pain (from 0 to 10), functional bladder capacity (FBC), voiding frequency at daytime and voiding frequency at night time as recorded in 3-day voiding diary.
- (2) Global response assessment (GRA) of satisfaction by the patient (categorized into -3, -2, -1, 0, 1, 2, 3, indicating markedly worse to markedly improved) at 1 month after the treatment day. An improvement of GRA by 2 scales at 1 month is considered effective.
- (3) Net changes of the maximum flow rate, voided volume and PVR from baseline to 1 month after the treatment day.

Voiding frequency at daytime and nighttime is measured as mean of the three-day voiding diary preceding the scheduled visit and the record days are 3 days.

Net change of each efficacy item will be analyzed by paired t-test between baseline and post-treatment in the treatment group and controlled group. The net changes of each efficacy item will be analyzed by ANOVA test to compare between treatment group and controlled groups. The global response assessment by the patients will be analyzed by Fisher exact test between the treatment and controlled groups.

All efficacy variables will be reported of respective point estimated and 95% confidence interval. Comparison tests will be reported of respective p value.

Secondary Safety Endpoints

- (1) Local adverse event incidences (hematuria, micturition pain, UTI, urinary retention) will be reported by both treatment group and controlled group and by physiological systems as appropriate. Incidence of adverse events and the categories of adverse event severity between treatments will be analyzed. The coding system used will be COSTART.

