- (2) The abnormalities of laboratory test results will be reported by patient list in the patients who have been tested for having severe adverse event.
- (3) The changes in physical examinations will be presented in the by-patient list.
- (4) All statistical tests used will be two-tailed with α = 0.05.

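### Urinary NGF and an uncounted set of cytokines form one secondary efficacy item with no lead analyte, adjustment or exploratory label, so its false-positive rate exceeds 5% and the plan sets no limit on it

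*Protocol*

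**What the plan says.** **Protocol.** Section 2 gives, as item (4) of the secondary efficacy endpoints, "Changes of urinary nerve growth factor and cytokines level from baseline to 1 month after treatment day". The follow-up block of the same section repeats it: "Changes of urinary nerve growth factor and cytokines level from baseline to 2 months after treatment day". NGF is the only analyte named. The number and identity of the cytokines are not given. On sampling, section 5.1 says "Urine samples (30 ml) will also be collected at each visit for analysis of the urinary NGF and cytokines levels", while the visit list in section 5.2 has urine for these assays at V1, V5, V6 and V7 only.

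**SAP.** The secondary efficacy list in 7.2 ends at item (3), the flow measures, and has no biomarker item. The statistical objective is superiority "with respect to the decreases of O'Leary-Sant symptom score, VAS, increase in functional bladder capacity and improvement in GRA", again with no biomarker. What remains are general rules:

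- Between arms: "The net changes of each efficacy item will be analyzed by ANOVA test to compare between treatment group and controlled groups".
- Within arms: "Net change of each efficacy item will be analyzed by paired t-test between baseline and post-treatment in the treatment group and controlled group".
- Significance level: "All statistical tests used will be two-tailed with α = 0.05". This stands in the safety list but is worded for all tests.
- Conclusions (7.1): "The primary conclusions will be made for the primary and secondary endpoints on the ITT patients".

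Neither document contains a multiplicity adjustment, a testing order, a lead analyte, a composite or an exploratory label for the biomarkers.

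**The concern.** One line in the endpoint list stands for a family of tests of unknown size. If each analyte counts as an efficacy item and is tested at 0.05, the error rate for the biomarker claim grows with the panel, and the panel can be fixed after the assays are run. The time point and the analyte to feature are also left open.

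What is at stake is a secondary claim. The primary endpoint, VAS and GRA are all patient-reported, so one cytokine below 0.05 could be taken as laboratory support for LESW. With about 50 patients and an open panel, that support could be chance.

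**Working it through.** **Inputs from the documents.** Two-sided 0.05 per test (SAP 7.2). Two biomarker time points defined as endpoints: 1 month and the follow-up assessment (Protocol section 2). Planned power for the primary 0.80, with a difference of 8.0 − 5.0 = 3.0, SD 5.0 and 25 per group (SAP 7.4). The plan states no error rate for the biomarkers, so there is no figure of its own to reproduce on this point.

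**Assumed, with a range.** The number of between-arm tests, k, and the common correlation between their test statistics, r, taken as 0, 0.5 and 0.8.

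**Step 1. Chance of at least one false positive when no analyte is affected.**

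For independent tests: 1 − 0.95^k.

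For common correlation r: 1 − ∫ φ(u) [Φ((1.96 − √r·u)/√(1−r)) − Φ((−1.96 − √r·u)/√(1−r))]^k du.

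| Tests | k | r = 0 | r = 0.5 | r = 0.8 |
|---|---|---|---|---|
| NGF + 1 cytokine, one time point | 2 | 9.8% | 9.1% | 7.8% |
| NGF + 4, one time point | 5 | 22.6% | 18.3% | 12.7% |
| NGF + 10, one time point | 11 | 43.1% | 30.4% | 18.0% |
| NGF + 4, two time points | 10 | 40.1% | 28.7% | 17.3% |

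For example, 1 − 0.95^5 = 1 − 0.774 = 0.226. Even the smallest panel at the highest correlation gives 7.8 / 5 = 1.56 times the stated level. The paired t-tests within each arm are not counted and would add further opportunities.

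**Step 2. When does a false positive become more likely than not?** At one time point with independent analytes, k = 13 gives 48.7% and k = 14 gives 51.2%. At r = 0.5 it takes about 30 (50.7%). At r = 0.8, 30 analytes still give only 26%.

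**Step 3. What would a gate on the primary do?** The plan has none, so this is hypothetical.

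- Primary truly null: a biomarker claim first needs a false-positive primary, so the rate is at most 5% for any k. Simulation gives 1.1% to 4.0% for k = 5 to 20 and r = 0 to 0.5.
- Primary effect real, biomarkers null and independent, k = 10: power × panel rate = 0.80 × 0.401 = 32%. At the 55% power that a two-sample t-test has with 25 per group and the SAP's own inputs, it is 0.547 × 0.401 = 22%.
- Once the primary has passed, the full rate in Step 1 applies.

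**The case against.** The best counter-argument is that the SAP plans no biomarker analysis at all. Its secondary list and objective leave NGF and cytokines out, and the phrase about each efficacy item follows directly on that list. On this reading the biomarker testing is undescribed rather than wrongly described. This stands in part: testing each analyte at 0.05 is an inference from general wording. But the protocol still makes the item an efficacy endpoint, the 0.05 rule is worded for all tests, and nothing in either document supplies a control. The omission is a defect in its own right.

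Some stronger readings are tempting, and the documents do not support them:

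- *A chance biomarker finding is likely.* This cannot be derived, because neither the number of analytes nor their correlation is given. Every figure in the Step 1 table is below one half.
- *All three post-treatment urine visits (V5, V6, V7) are tested.* Section 2 defines biomarker endpoints at two time points. V5 is a urine collection with no endpoint attached.
- *A gate on the primary would not help.* It would hold the error to 5% or less if the primary is truly null. It fails only within the panel once the primary is positive.
- *A biomarker would be the only evidence that is not self-reported.* Maximum flow rate, voided volume and PVR are also secondary endpoints. Nor does either document state an anti-inflammatory objective.

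**Conclusion.** The point holds in a limited form. The protocol has a biomarker efficacy item of unstated size, the SAP omits it, and the general rules that remain apply two-sided 0.05 with no control within the panel. The false-positive rate for a biomarker claim therefore exceeds 5% for any panel of two or more analytes that are not perfectly correlated, and the plan sets no upper limit.

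The excess may be modest or large: about 8 to 10% for two analytes at one time point, and 17 to 40% (29% at correlation 0.5) for five analytes at the two defined time points. These figures assume the panel size, a common correlation, no true effect on any analyte, and that each analyte is tested between arms at 0.05. The direction needs only the plural in the protocol and the 0.05 rule.

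This should be corrected, but it bears on secondary claims only. The primary analysis is not affected.

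**What to change.** 1. Add the biomarker item to SAP 7.2 so that it matches Protocol section 2.
2. In both places, make the between-arm difference in change of urinary NGF from V1 to V6 the single tested biomarker endpoint. NGF is the only analyte the protocol names, V1 is the pre-treatment sample and V6 is the primary endpoint visit.
3. Label all cytokines, and all other biomarker time points, exploratory.
4. List the cytokines to be assayed before unblinding. Report every one with its estimate, 95% confidence interval and a p value adjusted across the panel: Holm if the target is familywise error, Benjamini-Hochberg if it is the false discovery rate. Say which target is meant.
5. State that no efficacy conclusion rests on an unadjusted cytokine p value.
6. Reconcile the follow-up time point: the biomarker item in section 2 says 2 months, while V7 in section 5.2.8 is at 3 months.

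The cost is wording in the protocol and SAP, with no extra patients or samples. The one loss is that an isolated cytokine result can be reported only as exploratory.

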3. SHOCK WAVE MACHINE AND PROCEDURES

The shock wave applicator (“LITEMED” LM-ESWT-mini system, Taiwan) will be gently placed directly on the ultrasound transmission gel over the skin surface of suprapubic region above the urinary bladder during once a week for 4 weeks, with 2000 shocks, frequency of 3 pulses per second, and maximum total energy flow density 0.25 mJ/mm^2 . The current shock wave intensity and number used was modified from previous report [1, 2].

Eligible patients will be assigned a randomization number in sequential order and each of the randomization will determine the allocation of one of the two treatment groups (LESW and Placebo) in 1: 1 ratio as shown below. The LESW and placebo will be controlled by a research assistance who will not evaluate the therapeutic outcome to ensure the double-blind method.

Vital signs (body temperature, blood pressure, heart rate and respiration rate) will be recorded at pre-treatment and 30 minutes following treatment.

The treatment will be carried out in the out-patient clinic. Patient will be stayed in a treatment room and accompanied by a research assistant.

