5.2.2. Randomization and Treatment Visit (V1, Week 0)

5.2.2.1 Vital signs monitoring, check EKG and biochemistry results and confirm eligibility of patients.

5.2.2.2 A randomization number is given to eligible patient.

5.2.2.3 Inform patient of the possible adverse events.

5.2.2.4 Review three-day voiding diary.

5.2.2.5 Collect 30 ml urine for analysis of the urinary NGF and cytokines levels.

5.2.2.6 LESW given.

5.2.3. Treatment Visit (V2, Week 1, 1 week \pm 3 days after the V1 treatment day)

5.2.3.1 Vital signs monitoring, and confirm eligibility of patients.

5.2.3.2 LESW given.

5.2.4. Treatment Visit (V3, Week 2, 1 week \pm 3 days after the V2 treatment day)

5.2.4.1 Vital signs monitoring, and confirm eligibility of patients.

5.2.4.2 LESW given.

5.2.5. Treatment Visit (V4, Week 3, 1 week \pm 3 days after the V3 treatment day)

5.2.5.1 Vital signs monitoring, and confirm eligibility of patients.

5.2.5.2 LESW given.

5.2.5.3 Dispense three-day voiding diary to record for 3 days before the next visit day.

5.2.6 Evaluation Visit I (V5, 1 week \pm 3 days after the V4 treatment day)

5.2.6.1 Review patients voiding diary for urinary frequency, functional bladder capacity, and record reported VAS, O'Leary-Sant symptom score, and GRA.

5.2.6.2 Vital signs monitoring and record adverse events.

5.2.6.3 Check urinalysis for urinary tract infection if patient has symptoms.

5.2.6.4 Check uroflowmetry for maximum flow rate, voided volume, and PVR volume.

5.2.6.5 Appointment for the next visit at 1 month \pm 3 days after the V4.

5.2.6.6 Dispense three-day voiding diary to record for 3 days before the next visit day.

5.2.6.7 Collect 30 ml urine for analysis of the urinary NGF and cytokines levels.

5.2.7 Evaluation Visit II (Primary end-point, V6, 1 month \pm 7 days after the V4)

5.2.7.1 Review patients voiding diary for urinary frequency, functional bladder capacity, and record reported VAS, O'Leary-Sant symptom score, and GRA.

5.2.7.2 Vital signs monitoring and record adverse events.

5.2.7.3 Check urinalysis for urinary tract infection if patient has symptoms suggestive of urinary tract infection.

5.2.7.4 Perform Uroflowmetry study for maximum flow rate, voided volume and PVR volume.

5.2.7.5 Collect 30 ml urine for analysis of the urinary NGF and cytokines levels.

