5.2.8 Evaluation Visit III (V7, 3 month \pm 7 days after the V4)

5.2.8.1 Review patients voiding diary for urinary frequency, functional bladder capacity, and record reported VAS, O'Leary-Sant symptom score, and GRA.

5.2.8.2 Vital signs monitoring and record adverse events.

5.2.8.3 Check urinalysis for urinary tract infection if patient has symptoms suggestive of urinary tract infection.

5.2.8.4 Perform Uroflowmetry study for maximum flow rate, voided volume and PVR volume.

5.2.8.5 Collect 30 ml urine for analysis of the urinary NGF and cytokines levels.

5.2.8.6 Patients who do not respond to treatment will be provided with repeat LESW treatment optionally.

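### The protocol gives two rules for when non-responders receive repeat LESW, and one of them falls before the 3-month GRA endpoint, whose own time differs between protocol and SAP

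*Protocol*

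**What the plan says.** **Repeat treatment.** Protocol section 2, under Follow-up (3 months), states: "Patients who are not effective to the treatment at 2 months will receive repeated LESW treatment". The visit schedule, item 5.2.8.6, states: "Patients who do not respond to treatment will be provided with repeat LESW treatment optionally". That item is the last one listed for V7, after the diary review, scores, GRA, uroflowmetry and urine collection.

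**Visits.** After the last session (V4) the protocol schedules V5 at 1 week, then "Evaluation Visit II (Primary end-point, V6, 1 month" after V4, then "Evaluation Visit III (V7, 3 month" after V4. No visit carries a 2-month label.

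**GRA time.** The secondary endpoint in protocol section 2 reads "indicating markedly worse to markedly improved) at 3 months after the treatment day". The follow-up block of the same section reads "indicating markedly worse to markedly improved) at 2 months after the treatment day". SAP 7.2 sets GRA, and the definition of an effective result, at 1 month.

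**Which treatment is repeated.** Protocol section 3 separates the arms by name: "the allocation of one of the two treatment groups (LESW and Placebo) in 1: 1 ratio". The schedule then writes "5.2.2.6 LESW given" at V1, and the same at V2 to V4, for every randomized patient, including those on placebo.

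**Analysis of re-treated patients.** Neither document addresses it. SAP 7.3 covers incomplete observations only.

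**The concern.** The two repeat-treatment rules differ in time (2 months against 3) and in force (required against optional). Both are in current text. Under the section 2 rule, some patients would have begun a second course before the 3-month GRA, and before the V7 symptom score, VAS, diary, uroflowmetry and urinary markers. A 3-month comparison would then mix the effect of the four randomized sessions with that of a second course given selectively to patients who had not improved. It could not be read as the durability of the randomized treatment.

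Section 1 describes the trial as multicenter, so with two rules in print, centers could follow different ones. The unsettled GRA time adds to this. Unless one time is fixed before unblinding, it could be chosen after the data are seen, and only the later times are exposed to re-treatment.

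**Working it through.** The plan gives no figure to reproduce on this point. The check sets the texts side by side, places them on a time line, and works out the direction of any bias.

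**1. The rules compared**

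| | Section 2, Follow-up | Section 5.2.8.6 |
|---|---|---|
| Time | 2 months | V7, 3 months after V4 |
| Force | Required | Optional |
| Order relative to V7 measures | Before | Listed after |
| Treatment named | LESW | LESW |

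**2. Time line.** The protocol does not define the treatment day from which months are counted, so both V1 and V4 are tried. Nominal V4 is 3 × 7 = 21 days after V1. Taking a month as about 30.4 days, V6 is about day 30 after V4 and V7 about day 91, each ± 7 days.

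- Counted from V4, 2 months is about day 61 after V4.
- Counted from V1, 2 months is about day 61 − 21 = 40 after V4.

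On nominal dates, both fall after the latest V6 (30 + 7 = day 37) and before the earliest V7 (91 − 7 = day 84). So on either count the section 2 rule starts re-treatment after the primary endpoint visit and before V7. If the repeat is again four weekly sessions starting at 2 months (not stated), it ends 21 days later, at about day 82 or day 61. That is roughly 9 or 30 days before nominal V7, depending on the count.

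**3. Is there a visit at which to apply the section 2 rule?** Response is defined by GRA, which is scheduled at V5, V6 and V7 only. Counted from V4, nothing falls near 2 months. Counted from V1, V6 falls at about 21 + 30 = day 51, still short of day 61. The 2-month text therefore matches no scheduled visit and may be a leftover. Follow-up item (1) in the same block says 1 month under a 3-month heading, so the labels there are unreliable in general.

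**4. Direction of bias if patients are re-treated early.** Let p1 and p0 be the single-course response proportions at 3 months (LESW, placebo), u the share of non-responders re-treated before V7 (taken as equal in both arms), and s and r the response to the repeat among LESW and placebo non-responders. The observed proportions are

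- LESW: q1 = p1 + (1 − p1)·u·s
- placebo: q0 = p0 + (1 − p0)·u·r

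The difference therefore changes by u·[(1 − p1)·s − (1 − p0)·r].

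- *Active LESW repeated in both arms, s = r:* the change is −u·r·(p1 − p0). The difference narrows whenever LESW works.
- *Assigned treatment repeated:* the difference widens only if s/r exceeds (1 − p0)/(1 − p1); otherwise it narrows.

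A sign check with assumed values (not from the documents): p1 = 0.50, p0 = 0.20, u = 1, single-course difference 30 points.

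- Active repeat, s = r = 0.20: 0.60 v 0.36, difference 24 points.
- Assigned repeat, s = 0.20, r = 0.10: 0.60 v 0.28, difference 32 points.
- Assigned repeat, s = r = 0.10: 0.55 v 0.28, difference 27 points.

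The break-even ratio here is 0.80/0.50 = 1.6. These values show only that the sign depends on which treatment is repeated. They do not estimate the size.

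**5. What is not touched.** SAP 7.2 sets the primary endpoint and every listed secondary efficacy endpoint, GRA included, at 1 month.

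**The case against.** The strongest reply is that the 2-month text is a drafting remnant with no effect. It sits under a 3-month heading, beside an item labelled 1 month, and matches no scheduled visit. The only visit with an actual repeat-treatment step is V7, where that step comes last. If sites work from the visit schedule, the bias is zero. This stands as a plausible reading, and it is why the point is conditional. It does not remove the conflict: the follow-up block uses 2 months in items (2), (3) and (4) as well as in the re-treatment sentence, so it can also be read as a planned 2-month assessment followed by re-treatment.

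A second reply is that nothing the SAP tests is exposed. That is correct. What is exposed is the 3-month GRA, which the protocol lists as a secondary endpoint, together with the other V7 data.

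A third reply is that LESW names the active arm in section 3, so the repeat is active and the bias is conservative. That is the literal reading and should be given weight. The use of LESW at V1 to V4 for both arms keeps it from being certain.

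A reader might infer that the trial's main result is compromised, that the 3-month result is certainly biased toward no difference, or that a definite loss of power can be quoted. The documents support none of these. The primary endpoint precedes any re-treatment, the repeated treatment is not clearly identified, and no GRA response rate, repeat-response rate or re-treated share is given.

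**Conclusion.** The inconsistency is real and should be corrected, but its reach is limited. If section 2 is followed as written, re-treatment precedes the 3-month GRA secondary endpoint and the V7 measures, and a 3-month comparison no longer reflects the single randomized course. If section 5.2.8 is followed, or the 2-month figure simply means V7, the effect is zero. Between these cases the size cannot be computed from the documents.

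The expected direction is toward no difference if the repeat is active LESW and it works. If the assigned treatment is repeated, the difference could narrow or widen. Separately, the GRA time is stated as 3, 2 and 1 months in different places and needs one value whichever repeat rule applies. The 1-month primary endpoint and the efficacy analyses listed in the SAP stand as they are.

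**What to change.** 1. Replace the re-treatment sentence in protocol section 2 with: *Non-responders may be offered repeat treatment with active LESW only after all V7 (3-month) assessments are completed.* If the assigned treatment is meant, name that instead.
2. Before unblinding, set one GRA endpoint time in both documents. The simplest choice is 1 month (V6), which the SAP already tests, with 3 months (V7) as follow-up. Protocol section 2, secondary efficacy item (2), then changes from 3 months to 1 month, and items (1) to (4) under Follow-up (3 months) all change to 3 months.
3. Record the date of any repeat session. Keep the type of treatment with the research assistant who controls allocation and does not assess outcome, so that the record does not reveal the arm. Report by arm any re-treatment given before V7.

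**Cost.** One protocol sentence, a few time labels, two data fields and one reporting line, with no added patients or visits. The downside is that non-responders wait about one month longer than under the section 2 rule, but no longer than section 5.2.8 already provides.
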